### Appendix C: Relative Physician's Global Assessment

The relative PGA documents the physician's assessment of the subject's psoriasis status. Consideration should be given to the percent of body involvement as well as overall induration, scaling, and erythema. The PGA is assessed relative to baseline condition and is defined as: (1) = clear, (2) = excellent, (3) = good, (4) = fair, (5) = poor, and (6) = worse. The following table further defines the rating.

Rating	% Clearing	Definition of Response
1 = Clear	100% clear	Some residual pinkness or pigmentation: Woronoff's ring may be present.
2 = Excellent	75 to 99% clearing	Marked improvement: nearly normal skin texture; some erythema may be present.
3 = Good	50 to 74% clearing	Moderate improvement: plaque has cleared to point of small scattered papules with normal intervening epidermis.
4 = Fair	25 to 49% clearing	Slight improvement: decrease in scaling and softening of plaque.
5 = Poor	0 to 24% clearing	Little or no change in scaling, erythema, or plaque elevation.
6 = Worse		Worse

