Another subcutaneous agent, ustekinumab, has been approved for the same indication. Ustekinumab is a human IL-12 and IL-23 antagonist indicated for the treatment of adult patients

(18 years or older) with moderate to severe chronic plaque psoriasis who are candidates for phototherapy or systemic therapy. An increase of infections and a few cases of skin cancer were reported in 2 large placebo-controlled studies.

One oral agent, apremilast (an inhibitor of phosphodiesterase 4), has been approved for the treatment of adult patients with moderate to severe chronic plaque psoriasis who are candidates for phototherapy or systemic therapy. However, safety concerns such as depression, weight decrease, and issues with drug interactions due to a strong cytochrome P450 enzyme induction have been reported. Also, administration requires a titration at initiation due to gastrointestinal (GI) side effects. The efficacy at 16 weeks was relatively less than that observed secukinumab and ustekinumab. In 2 large controlled studies, efficacy results were PASI 75 of 33.1% and 28.8% versus placebo 5.3% and 5.8%, with the static Physician Global Assessment (sPGA) of “clear” or “almost clear” of 21.7% and 20.4% versus placebo 3.9% and 4.4%, respectively. Apremilast is also approved for psoriatic arthritis.

Several Janus kinase (Jak) inhibitors have been studied for the therapy of psoriasis as well as other autoimmune diseases. However, none has been approved for the treatment of psoriasis to date. Tofacitinib is an inhibitor of Jak 3 with somewhat less activity against Jak 1 and Jak 2. It has been approved by the Food and Drug Administration (FDA) as a twice daily (BID) oral medication for the therapy of rheumatoid arthritis and is marketed as XELJANZ®, and has multiple severe infectious and immunologic side effects associated with therapy. Monotherapy with tofacitinib was associated with a modest increase in American College of Rheumatology 20% (ACR20) improvement criteria compared with placebo (57% versus 26%). Ruxolitinib is a Jak 1 and Jak 2 inhibitor that has been approved for myelofibrosis. It has also been associated with severe side effects including bone marrow suppression. Both of the above Jak inhibitors have undergone initial clinical testing in psoriasis, but the side effect profile of this class of inhibitors has been troublesome.

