#### **7.2.11 Relative Physician's Global Assessment**

The relative PGA documents the physician's assessment of the subject's psoriasis status (Robinson 2012). Consideration should be given to the percent of body involvement as well as overall induration, scaling, and erythema (refer to Appendix C).

The DLQI is a skin disease-specific instrument designed to assess the impact of the disease on a subject's quality of life (Finlay et al, 1994). Refer to Appendix D for the complete questionnaire.

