### **12.7 Efficacy Analysis**

The primary efficacy endpoint for analyses will be the number (%) of subjects with a 75% decrease in PASI by Week 16.

The secondary efficacy endpoints for analysis will include the following:

1. A 50% reduction in Week 16 PASI score (PASI 50)
2. The mean Week 16 percent change from baseline in PASI
3. Improvements in PGA of “clear” or “almost clear” at Week 16
4. Improvements in DLQI at Week 16

The exploratory efficacy endpoints are:

- To evaluate the concentration and changes in IL-17 expression in blood, tissue, and other biomarkers in punch biopsies after 16 weeks of dosing with KD025

Efficacy analyses will be divided into 2 periods: the double-blind treatment period through database lock at Week 16 and the open-label, 32-week continuation period.

Efficacy analyses will include the number (%) of subjects with a 75% decrease in PASI (number of subjects that reach PASI 75) at Week 16 in the KD025 treatment groups compared with the placebo group in a pairwise manner using a Fisher’s Exact test. The number of subjects who reach PASI 50 at Week 16 will be analyzed similarly. Treatment group differences in DLQI and PGA changes from baseline to Week 16 will be assessed using an analysis of covariance (ANCOVA) model with treatment as a fixed effect and a subject’s baseline value as a covariate.

No adjustments for multiplicity are being made for this Phase 2 study.

For further details, see the statistical analysis plan (SAP).

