3.8.2 Secondary Endpoints

- The Week 16 change from baseline in PASI scores
The descriptive statistics (n, mean, 95% CI) of Week 16 change from baseline in PASI scores will be summarized and tabulated by treatment groups.
- The Week 16 percent change from baseline in PASI
The descriptive statistics (n, mean, 95% CI) of Week 16 percent change from baseline in PASI scores will be summarized and tabulated by treatment groups.
- Improvements in PGA of “clear” or “almost clear” (excellent) at Week 16
Use the same approach with primary endpoint analysis in section 3.8.1.
- Improvements in DLQI at Week 16
The descriptive statistics (n, mean, 95% CI) of DLQI changes from baseline to Week 16 will be summarized and tabulated by treatment.
- The Week 48 change from baseline in PASI scores
The descriptive statistics (n, mean, 95% CI) of Week 48 change from baseline in PASI scores will be summarized and tabulated by treatment groups.
- The Week 48 percent change from baseline in PASI
The descriptive statistics (n, mean, 95% CI) of Week 48 percent change from baseline in PASI scores will be summarized and tabulated by treatment groups.
- The Week 48 change from Week 16 in PASI scores
The descriptive statistics (n, mean, 95% CI) of Week 48 change from Week 16 in PASI scores will be summarized and tabulated by treatment groups.

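### The secondary endpoint 'PGA clear or almost clear' does not match the relative PGA that the trial uses, and the protocol's baseline-adjusted ANCOVA of PGA has no defined baseline value

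*Protocol*

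**What the plan says.** **Instrument.** Protocol 7.2.11 names one scale: "The relative PGA documents the physician's assessment of the subject's psoriasis status". It points to Appendix C, which states that "The PGA is assessed relative to baseline condition" and lists the ratings as "1) = clear, (2) = excellent, (3) = good, (4) = fair, (5) = poor, and (6) = worse". Rating 2, excellent, is "75 to 99% clearing", with a descriptor of marked improvement and skin texture close to normal. Rating 5, poor, covers 0 to 24% clearing and is described as "Little or no change in scaling, erythema, or plaque elevation".

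**Endpoint.** The protocol synopsis, 5.5 and 12.7 list PGA 'clear' or 'almost clear' at Week 16 as a secondary efficacy endpoint, with no mapping to the Appendix C ratings. SAP 3.8.2 words it as "Improvements in PGA of “clear” or “almost clear” (excellent) at Week 16", and SAP Table 3 repeats the parenthesis for Weeks 16 and 48.

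**Analysis.** Protocol 12.7, like the synopsis, says: "Treatment group differences in DLQI and PGA changes from baseline to Week 16 will be assessed using an analysis of covariance (ANCOVA) model". Cohort is the factor in that model, and each subject's own baseline score is the covariate. Table 1-1 schedules PGA scoring at Week 1 Day 1. SAP 3.8.2 has no PGA ANCOVA. It applies the primary-endpoint method of SAP 3.8.1: Fisher's exact test of each dose against placebo, with subjects lacking a Week 16 assessment counted as failures.

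**Background.** Protocol section 4 reports results for the approved oral agent "with the static Physician Global Assessment (sPGA) of" clear or almost clear: 21.7% and 20.4%, versus 3.9% and 4.4% on placebo.

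**The concern.** 'Clear or almost clear' describes a state of the skin at a visit. The Appendix C ratings describe how far a subject has moved from where that subject began. Reporting the second under the name of the first tells the reader that something was measured which was not. The protocol's background uses the same words for a static scale, so the label also invites a comparison that the instrument cannot support.

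The ANCOVA raises a separate problem. A rating that is already a comparison with baseline has no evident meaning at baseline. Both the change score and the covariate therefore depend on a quantity that the protocol does not define. With the ANCOVA still in the protocol and a different analysis in the SAP, it is unclear which PGA result was planned.

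**Working it through.** The documents give no rate, effect size or power for the PGA endpoint, so there is no stated figure to reproduce. The check sets the endpoint against the scale, then tests whether the protocol's model can be fitted.

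**1. Endpoint terms against Appendix C**

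| Endpoint term | Appendix C rating | Meaning on that scale |
|---|---|---|
| clear | 1 = clear | 100% clear |
| almost clear | none; the SAP substitutes 2 = excellent | 75 to 99% clearing versus baseline |

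One of the two terms is a rating. Under the SAP the responder set is ratings 1 and 2, that is, 75 to 100% clearing relative to the subject's own baseline.

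**2. The protocol's ANCOVA**

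Write Y for the Week 16 rating, B for the baseline rating and g for the cohort (5 cohorts of about 22, 110 in total). The model in 12.7 is

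Y − B = μ + τ_g + βB + error.

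Its design matrix has 1 intercept + 4 treatment contrasts + 1 covariate = 6 columns. Appendix C does not say what B is, so there are three cases.

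- *Every subject is rated 5 on Day 1* (no change, hence 0% clearing). The covariate column is 5 times the intercept column. The matrix has 6 columns but rank 5, so β cannot be estimated. With the covariate dropped, the outcome is Y − 5, and the contrast of dose g with placebo is (mean Y_g − 5) − (mean Y_placebo − 5) = mean Y_g − mean Y_placebo. This is a one-way ANOVA of the Week 16 rating with no baseline adjustment. A numerical check with 5 × 22 subjects and simulated ratings gave rank 5 and identical contrasts for change and for the raw rating.
- *No rating is recorded on Day 1.* Y − B and B are both missing and the model cannot be fitted.
- *Sites enter some absolute severity judgement on Day 1.* The documents do not ask for this. If it happened, Y − B would subtract two different constructs.

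**3. Protocol against SAP**

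Protocol 12.7 lists the PGA responder endpoint but names no test for that proportion; its only PGA-specific method is the ANCOVA of change. SAP 3.8.2 gives the responder proportion a test and omits the ANCOVA. The SAP analysis needs only the Week 16 rating, so it is well defined on this scale. No reason for the switch is given.

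**The case against.** Much of the defence stands.

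- 'Clear' is on the scale, so only the 'almost clear' half of the endpoint is missing.
- The 'excellent' row is more than a percentage band. Its descriptor speaks of nearly normal texture with some redness, so the SAP's mapping is reasonable, and it is printed openly in 3.8.2 and Table 3.
- The protocol defers to the SAP for full analysis details, and the SAP has already dropped the ANCOVA. What remains is protocol wording that was never reconciled.
- All arms are rated on the same scale, so the label does not bias the contrast with placebo. No comparison with the approved oral agent is planned, and the background figures are plainly marked as static.

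The descriptor does not turn the rating into an absolute state, however. The row also says marked improvement, its band starts at 75%, and the whole scale is declared relative to baseline.

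A reader might be tempted to go further in three ways, and the documents support none of them.

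1. *Sizing the effect of the label from the cited studies.* There PASI 75 exceeded static clear/almost clear by 33.1 − 21.7 = 11.4 and 28.8 − 20.4 = 8.4 points. Neither measure is the relative PGA, and the drug is another one. The gap does not predict this endpoint.
2. *Treating the endpoint as PASI 75 again, or arguing from residual PASI.* A 75% reduction from PASI 48 leaves 0.25 × 48 = 12, the entry threshold, but from PASI 12 it leaves 0.25 × 12 = 3. Either figure assumes that percent clearing equals percent PASI reduction, which the documents never say.
3. *Concluding that the label would create part of an apparent advantage for the drug.* No planned analysis makes the comparison that this would require.

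**Conclusion.** The point holds as a mismatch between endpoint and instrument, together with an unreconciled difference between protocol and SAP. As written, a named secondary endpoint would be reported as an absolute state when it measures at least 75% clearing from baseline. The result can support a statement about relative response against placebo. It cannot support a statement about the proportion reaching an almost-clear state, or a reading against the static rates of 21.7% and 20.4%.

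The protocol's PGA ANCOVA cannot deliver the baseline adjustment it promises on this scale. With a constant Day 1 rating of 5 the treatment contrasts remain estimable, but the covariate does nothing; with no Day 1 rating there is no model. This defect is in the protocol only.

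The scope is one of four secondary efficacy endpoints. PASI 75 is untouched and the randomised PGA comparison stays valid. No shift in percentage points can be derived from the documents. The conclusion assumes that sites used Appendix C as written, since the documents contain no other PGA scale.

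**What to change.** 1. In the protocol synopsis, 5.5 and 12.7, and in SAP 3.8.2 and Table 3, rename the endpoint 'relative PGA clear or excellent (ratings 1-2, at least 75% clearing versus baseline)'.
2. Add one sentence to the SAP, carried into the study report, that this endpoint is not comparable with a static PGA of clear or almost clear.
3. Remove PGA from the ANCOVA sentence in the synopsis and 12.7, leaving DLQI, so that the SAP's Fisher responder comparison governs. Record the reason for the change in the SAP. The secondary objective on PGA changes is still served, because the Week 16 rating is itself a measure of change.
4. State that any Day 1 PGA entry is not used as a baseline score.

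Reporting 'clear' (rating 1) as a separate row is optional.

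The cost is wording in two documents, and one table row if the option is taken; no new data are needed. The sponsor gives up the familiar 'clear or almost clear' label. Specifying a static PGA with its own Day 1 score would be the other route, but SAP 3.12 reports the study as terminated early with 110 subjects, so it could not realistically be added now.

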**Appendix D: Dermatology Life Quality Index**

**The aim of this questionnaire is to measure how much your skin problem has affected your life OVER THE LAST WEEK. Please tick  one box for each question.**

- |           |  |  |     |
|-----------|--|--|-----|
| 1. | Over the last week, how itchy, sore, painful or stinging has your skin been?   | Very much 
A lot 
A little 
Not at all  |     |
| 2. | Over the last week, how embarrassed or self-conscious have you been because of your skin?  | Very much 
A lot 
A little 
Not at all  |     |
| 3. | Over the last week, how much has your skin interfered with you going shopping or looking after your home or garden ?
relevant  | Very much 
A lot 
A little 
Not at all  | Not |
| 4. | Over the last week, how much has your skin influenced the clothes you wear?
relevant   | Very much 
A lot 
A little 
Not at all  | Not |
| 5. | Over the last week, how much has your skin affected any social or leisure activities?
relevant                                        | Very much 
A lot 
A little 
Not at all  | Not |
| 6. | Over the last week, how much has your skin made it difficult for you to do any sport ?
relevant    | Very much 
A lot 
A little 
Not at all  | Not |
| 7. | Over the last week, has your skin prevented you from working or studying ?
relevant   | Yes 
No   | Not |
|           | If "No", over the last week how much has your skin been a problem at work or studying ?  | A lot 
A little 
Not at all                                        |     |

- 
8. Over the last week, how much has your skin created problems with your **partner** or any of your **close friends** or **relatives**?  
relevant
- Very much   
A lot   
A little   
Not at all  Not
9. Over the last week, how much has your skin caused any **sexual difficulties**?  
relevant
- Very much   
A lot   
A little   
Not at all  Not
10. Over the last week, how much of a problem has the **treatment** for your skin been, for example by making your home messy, or by taking up time?  
relevant
- Very much   
A lot   
A little   
Not at all  Not

**Please check you have answered EVERY question. Thank you.**

**Appendix E: Clinical Symptom and Adverse Event Grading Scale**

CLINICAL ADVERSE EVENT GRADING		
Severity	Grade	Definition
Mild	1	Awareness of symptom, but easily tolerated. Usually transient requiring no special treatment; does not interfere with usual status or activities
Moderate	2	May be ameliorated by simple therapeutic measures; may interfere with usual activities
Severe	3	Incapacitating; unable to perform usual activities
Life-threatening	4	Requires immediate intervention; need for emergency treatment
Death	5	Resulting in the subsequent death of the subject

---

## Appendix F: Clinical Adverse Events: Determining Relationship to Study Drug

### 1 NOT RELATED

This category applies to those AEs which, after careful medical consideration, are clearly felt to be due to extraneous causes (disease, environment, etc.) that are unrelated to the administration of study drug.

### 2 UNLIKELY RELATED (must have first 2)

This category applies to those AEs which, after careful medical consideration, are felt unlikely to be related to the administration of the study drug. The relationship of an AE to the study drug can be considered unlikely if:

- It does not follow a reasonable temporal sequence from administration of the drug.
- It could readily have been a result of the subject's clinical state, environmental or toxic factors, or other modes of therapy administered to the subject.
- It does not follow a known response pattern to the suspected drug.
- It does not reappear or worsen when the drug is re-administered.

### 3 POSSIBLY RELATED (must have first 2)

This category applies to those AEs which, after careful medical consideration, are felt unlikely to be related to the administration of the study drug, but the possibility cannot be ruled out with certainty. The relationship of an AE to the study drug can be considered possible if:

- It follows a reasonable temporal sequence from administration of the drug.
- It could readily have been a result of the subject's clinical state, environmental or toxic factors, or other modes of therapy administered to the subject.
- It follows a known response pattern to the suspected drug.

### 4 PROBABLY RELATED (must have first 3)

This category applies to those AEs which, after careful medical consideration, are felt with a high degree of certainty to be related to the administration of the study drug. The relationship of an AE to the study drug can be considered probable if:

- It follows a reasonable temporal sequence from administration of the drug.
- It could not be reasonably explained by the known characteristics of the subject's clinical state, environmental or toxic factors or other modes of therapy administered to the subject.
- It disappears or decreases upon cessation of drug or reduction in dose.\*
- It follows a known response pattern to the suspected drug.

**5 DEFINITELY RELATED** (must have first 3)

This category applies to those AEs, which, after careful medical consideration, are felt to be related to the administration of the study drug. The relationship of an AE to the study drug can be considered related if:

- It follows a reasonable temporal sequence from administration of the drug or drug levels have been established in body fluids or tissues.
- It could not be reasonably explained by the known characteristics of the subject's clinical state, environmental or toxic factors or other modes of therapy administered to the subject.
- It disappears or decreases upon cessation of drug or reduction on dose and appears upon rechallenge.\*
- It follows a known response pattern to the suspected drug.

\*There are exceptions when an AE does not disappear upon discontinuation of the drug, yet drug relatedness clearly exists.

Cobert, B. (2012). *Cobert's Manual of Drug Safety and Pharmacovigilance* (2nd ed.). Massachusetts: Jones & Bartlett Learning, LLC.

**Appendix G: CYP3A4 Inducers and inhibitors**

Use of these drugs should be avoided in subjects who are receiving KD025 unless deemed clinically necessary (Flockhart 2007):

Inhibitor/Inducer	Drug Name
Inhibitors	indinavir a nelfinavir a ritonavir a clarithromycin a itraconazole a ketoconazole a nefazodone a erythromycin b grapefruit juice b verapamil b suboxone b diltiazem b cimetidine c amiodarone fluvoxamine troleandomycin voriconazole
Inducers	carbamazepine efavirenz nevirapine phenobarbital phenytoin pioglitazone rifabutin rifampin St. John's Wort troglitazone

- a. A Strong inhibitor is one that causes a > 5-fold increase in the plasma AUC values or more than 80% decrease in clearance.
- b. A Moderate inhibitor is one that causes a > 2-fold increase in the plasma AUC values or 50-80% decrease in clearance.  
 A Weak inhibitor is one that causes a > 1.25-fold but < 2-fold increase in the plasma AUC values or 20-50% decrease in clearance.

1 INTRODUCTION

Psoriasis is an autoimmune disease that affects many parts of the body but is primarily manifested in the skin. It affects 2% to 3% of the population globally, making it a very common inflammatory autoimmune disease. A number of biologic products have been approved for the treatment of moderate to severe chronic plaque psoriasis. However, there are still safety concerns and most of these products are parenterally administered. An oral agent such as KD025, which targets IL-17, could potentially provide an oral treatment option with an improved safety and efficacy profile.

This Statistical Analysis Plan (SAP) describes statistical procedures to be used for study KD025-211 as specified in the protocol (Amendment No. 2, 12-Mar-2019). The pharmacodynamic data will be analyzed and reported separately.

The SAP was written in accordance with the recommendations outlined in the International Conference on Harmonization (ICH) E9 Guideline entitled “Guidance for Industry: Statistical Principles for Clinical Trials” and the most recent ICH-E3 Guideline, entitled “Guidance for Industry: Structure and Content of Clinical Study Reports.”

2 STUDY SUMMARY

2.1 Study Objectives

2.1.1 Primary Objective

- To assess the number of subjects that reach Psoriasis Area and Severity Index (PASI) 75 after 16 weeks of dosing with various regimens of KD025 compared with placebo

